9.2 Day 1 (\pm 3 Days) of Subsequent Cycles

The following evaluations and procedures will be performed on Day 1 of subsequent cycles. All assessments should be performed prior to vopratelimab dosing, unless otherwise noted.

- Physical examination.
- Vital signs pre-and post-infusion.
- Weight.
- Pregnancy test for women of childbearing potential.
- Laboratory assessments including hematology and chemistry; additional laboratory measurements may be performed in accordance with institutional guidelines.
- Concomitant medication review.
- AE assessment.
- Study treatment (vopratelimab \pm partner drug) administration on the same dose and schedule as a subject was receiving at the time of discontinuation from the parent study. Any changes to the dose and schedule of vopratelimab must be in accordance with a dose and schedule previously shown to be safe and well tolerated and must be discussed with the medical monitor. Any changes to the dose and schedule of nivolumab or ipilimumab must be discussed with the medical monitor.
- Disease imaging (e.g., CT scan) for response assessment in accordance with [Section 9.2.3](#).

9.2.1 Subsequent Dosing Days

Subjects should continue to receive study drug administration dosing within every cycle per the dose and schedule administered in the parent study. Any changes to the dose and schedule of vopratelimab must be in accordance with a dose and schedule previously shown to be safe and well tolerated and must be discussed with the medical monitor. Any changes to the dose and schedule of nivolumab or ipilimumab must be discussed with the medical monitor.

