| Inclusion Criteria | 
Subject is currently receiving and tolerating vopratelimab therapy and receiving clinical benefit from study treatment in the opinion of the Investigator and/or Sponsor.
 
Subject has demonstrated compliance with the parent study requirements, as assessed by the Investigator and/or Sponsor, and is able and willing to comply with the necessary visits and assessments as part of the rollover study.
 
Written informed consent must be obtained prior to enrolling in the rollover study and receiving study treatment. If consent cannot be expressed in writing, it must be formally documented and witnessed, ideally via an independent trusted witness.
 
Women of childbearing potential and males with partners of child-bearing potential must agree to use adequate birth control throughout their participation and for 5 months following the last study treatment.
 |

| | |
|---|---|
| Exclusion Criteria | 
Subject was permanently discontinued from the parent study due to unacceptable toxicity, non-compliance with study procedures, withdrawal of consent, or any other reason.
 
Subject is receiving concurrent anticancer treatment (excluding combination drugs such as nivolumab or ipilimumab as a component of the combination dosing regimen used in the parent study).
 
Women who are pregnant or breastfeeding.
 
Subject has any medical or social condition that, in the opinion of the Investigator, might place a subject at increased risk, affect compliance, or confound safety or other clinical study data interpretation.
 |
| Efficacy Assessments | 
The antitumor activity of study treatment will be assessed using Response Evaluation Criteria in Solid Tumors (RECIST) version 1.1 as assessed by the local Investigator and based on imaging performed according to institutional standard of care guidelines, but at least every 6 months (\pm 3 weeks).
 |
| Safety Assessments | 
Safety will be monitored through adverse event (AE) documentation, clinical laboratory evaluations, physical examinations, and vital signs performed at every visit. Safety and tolerability will be assessed by the incidence and severity of AEs and serious adverse events (SAEs) as determined by the current version of the Common Terminology Criteria for Adverse Events (CTCAE). Immune-related AEs will also be assessed.
 |

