5.4 Reproductive Restrictions

There are no data regarding the effect of vopratelimab on the unborn fetus. Vopratelimab should not be administered to pregnant women. Embryo-fetal toxicity is a labeled warning for nivolumab and ipilimumab ([Opdivo® Full Prescribing Information {Bristol-Myers Squibb Company 2021}](#), [Yervoy® Full Prescribing Information {Bristol-Myers Squibb Company 2021}](#)). Women of childbearing potential must have a negative serum or urine pregnancy test prior to administration of each dose of vopratelimab throughout the study. Women of childbearing potential and males with partners of childbearing potential must agree to use adequate birth control throughout their participation and for 5 months following the last study treatment.

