6 STUDY TREATMENTS AND ADMINISTRATION

6.1 Study Drug Dosage and Administration

For this study, the investigational drug refers to vopratelimab, which will be supplied by the Sponsor, Jounce Therapeutics. Study drug(s) refer to vopratelimab and any partner drugs administered in the parent study (e.g., nivolumab, ipilimumab).

All dosages prescribed and dispensed to subjects and all dose changes during the study must be recorded on the Dosage Administration Record electronic case report form (eCRF).

For all study medication administration, a physician must be present at the site or immediately available to respond to emergencies during all administrations of all study medications. Note that the infusion time is not inclusive of the flush post study drug administration.

Vopratelimab is administered as a single agent or in combination with nivolumab or in sequence with ipilimumab at a subject's prior identified tolerable dose regimen and schedule. Any changes to the dose and schedule of the study agents must be discussed with the medical monitor as stated in [Section 3](#).

When vopratelimab is administered on the same day as nivolumab, vopratelimab should be dosed first with a 30-minute (-5/+10 minutes) evaluation period prior to administration of combination therapy. In instances where an infusion reaction occurs during dosing of vopratelimab, administration of combination therapy may be delayed beyond the 30-minute (-5/+10 minutes) evaluation period.

If treating in sequence with ipilimumab, continue to follow dosing guidelines from the parent study for up to 4 doses. Administer ipilimumab as a 90-minute IV infusion or per the approved label infusion time (-5/+10 minutes) at a dose of 3 mg/kg q6w for up to 4 doses. Note that the approved schedule for ipilimumab administration is q3w; this protocol administers ipilimumab at a less frequent schedule. Additional doses of ipilimumab beyond 4 doses total may be considered on a patient by patient basis in consultation with the medical monitor.

Further instructions for the preparation and dispensation of vopratelimab, nivolumab, and ipilimumab are described in the Study Pharmacy Manual.

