10.7 Pregnancy Test

A serum or urine pregnancy test must be performed and reviewed on all women of childbearing potential prior to every dose of study drug. Test results will be recorded on the eCRF.

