14 APPENDICES

Appendix 1: Schedule of Events (Every 6 Week Administration)

| | Rollover Entry/Cycle 1 Day 1 ¹ | Day 1 (\pm 3 days) of Subsequent Cycles ² | Rollover End of Study |
|---|---|---|--------------------------|
| Timing of Visit | | | |
| Informed Consent | X | | |
| Eligibility Criteria | X | | |
| Physical Examination ³ | X | X | X |
| Weight (kg) | X | X | X |
| Vital Signs ⁴ | X | X | X |
| Pregnancy Test ⁵ | X | X | |
| Hematology | X | X | X |
| Chemistry | X | X | X |
| Other Laboratory Assessments per Standard of Care | X | X | X |
| Blood Samples for Pharmacodynamic Biomarkers | X | X ⁶ | X |
| Study Treatment Administration ⁷ | X | X | |
| Disease Imaging (e.g., CT scan) | | X ⁸ | X ⁸ |
| Concomitant Medications | X | X | X |
| Adverse Events | X | X | X |

Abbreviations: CT = computed tomography; ; RECIST = Response Evaluation Criteria in Solid Tumors

Footnotes:

¹ Enrollment into the rollover study should occur upon exit from the parent study to avoid any interruptions in study treatment administration.

² All assessments should be performed prior to vopratelimab dosing, unless otherwise noted.

³ Targeted physical examination is required at each study administration visit and at the End-of-study visit.

⁴ Vital signs to include temperature, heart rate, respiratory rate, blood pressure, and oxygen saturation. Vital signs should be taken prior to and at the end of each vopratelimab infusion.

⁵ Negative serum or urine pregnancy test for women of childbearing potential prior to administration of vopratelimab on Day 1 of each treatment cycle.

⁶ Blood sampling for exploratory analyses of pharmacodynamic biomarkers should be collected approximately every 3 months (\pm 4 weeks) at the time of a scheduled clinic visit. Sample collection may be discontinued at any time per the Sponsor's discretion. Please refer to the Study Laboratory Manual for more details.

⁷ Study treatment (vopratelimab \pm partner drug) should be administered on the same dose and schedule as a subject was receiving at the time of discontinuation from the parent study. Any changes to the dose and schedule of vopratelimab must be in accordance with a dose and schedule previously shown to be safe and well tolerated and must be discussed with the medical monitor. Any changes to the dose and schedule of nivolumab or ipilimumab must be discussed with the medical monitor.

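### The pregnancy-test rule in Section 10.7 covers every partner-drug dose, but Section 5.4 and footnote 5 of both schedules cover only vopratelimab doses

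*Protocol*

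**What the plan says.** Three parts of the protocol set the scope of pregnancy testing in women of childbearing potential.

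- Section 10.7: "A serum or urine pregnancy test must be performed and reviewed on all women of childbearing potential prior to every dose of study drug". Section 6.1 defines the term: "Study drug(s) refer to vopratelimab and any partner drugs administered in the parent study (e.g., nivolumab, ipilimumab", and it keeps the separate term investigational drug for vopratelimab.
- Section 5.4: "Women of childbearing potential must have a negative serum or urine pregnancy test prior to administration of each dose of vopratelimab throughout the study". The same section records that "Embryo-fetal toxicity is a labeled warning for nivolumab and ipilimumab".
- Footnote 5, worded alike in Appendices 1 and 2: "Negative serum or urine pregnancy test for women of childbearing potential prior to administration of vopratelimab on Day 1 of each treatment cycle".

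On the timing of visits, Section 9.2 opens with "The following evaluations and procedures will be performed on Day 1 of subsequent cycles" and includes a pregnancy test in its list. Section 9.2.1, headed Subsequent Dosing Days, says "Subjects should continue to receive study drug administration dosing within every cycle per the dose and schedule administered in the parent study" and then deals only with dose changes; it lists no assessment. Each schedule has three columns: entry (Cycle 1 Day 1), Day 1 of later cycles, and end of study.

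The synopsis, under Safety Assessments, refers to "clinical laboratory evaluations, physical examinations, and vital signs performed at every visit".

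**The concern.** A pregnancy test protects only if it is done before the dose that carries the risk. Section 5.4 acknowledges the risk for both partner drugs, yet it ties the test to vopratelimab alone. The schedule of events is the page a site usually works from, and it carries the narrowest rule. If a partner drug is given on its own, the wider rule is found only in Section 10.7, and it depends on a definition given in Section 6.1. Section 10.8.7 requires a pregnant participant to be withdrawn, so a missed test could also delay a withdrawal that the protocol calls for.

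A smaller point sits beside it. Section 9.2.1 does not say what, if anything, is to be measured on a dosing day other than Day 1. The synopsis can be read as asking for laboratory tests and vital signs on such a day, and Section 9 and the schedules do not say whether it does.

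**Working it through.** The plan gives no figure on this point, so the check is a comparison of texts.

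**Step 1. Can a partner drug be given without vopratelimab?** Three places imply it. Section 9.2 already covers Day 1 administration of vopratelimab with or without a partner, so Section 9.2.1 would add little unless it meant other days within the cycle. Section 6.1 sets the order of infusions conditionally, for occasions when vopratelimab and nivolumab fall on the same day. Section 6.1 also describes ipilimumab as given in sequence. No section specifies such a day, and the regimens themselves are in the parent protocols.

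**Step 2. Apply each rule to the same dose.**

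| Dose | Section 10.7 with 6.1 | Section 5.4 | Footnote 5, Appendices 1 and 2 |
|---|---|---|---|
| Vopratelimab on Day 1, with or without partner | Test | Test | Test |
| Vopratelimab on another day | Test | Test | Silent |
| Partner drug on a day without vopratelimab | Test | Silent | Silent |

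The rules agree on the first row and diverge on the last. A site that follows Section 10.7 meets all of them. A site that follows footnote 5 does not meet Section 10.7.

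**Step 3. Does the result depend on reading 10.7 through 6.1?** Section 10.7 uses the singular, study drug. If that meant vopratelimab only, Section 10.7 would agree with Section 5.4, and no section would require a test before a partner-only dose, despite the label warning noted in 5.4. The 6.1 definition makes the wider reading the better one, but either reading leaves something to correct.

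**Step 4. How old could the last test be?** Assume vopratelimab and its test fall on Day 1 of every cycle, with no delay and visit windows set aside. A partner-only dose within the cycle then comes less than 6 × 7 = 42 days after a test under Appendix 1, and less than 3 × 7 = 21 days under Appendix 2.

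**Step 5. Laboratory tests and vital signs.** Section 10.5 gives no visit timing for laboratory tests, and Section 10.2 times vital signs by the vopratelimab infusion. The only text that might place either on a partner-only day is the synopsis clause. By contrast, examination (10.1), adverse events (10.8.2), concomitant medication (6.1.2) and weight (10.3) have an every-visit rule in the body and are not in question.

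**The case against.** The strongest reply is that the affected dose is not shown to exist. Where the protocol places treatment in a visit (Sections 9.1 and 9.2, and footnote 7 of both schedules), it speaks of vopratelimab with or without a partner, at entry or on Day 1. Whether any parent regimen departs from that cannot be seen here. This stands, and it is why the point is conditional.

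Second, the rules are additive. Nothing in Section 5.4 or footnote 5 exempts a partner-only dose, and Section 10.7 is the dedicated section and uses mandatory wording. This also stands. A reader might infer that the protocol contradicts itself or allows untested dosing. It does neither: the requirement exists, and the fault is that the schedule does not show it.

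Third, women of childbearing potential are tested at entry and on Day 1 of each cycle, and must use contraception throughout and for 5 months after the last treatment. That lowers the risk but does not replace the test that Section 10.7 requires.

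On laboratory tests and vital signs, a reader might infer that the synopsis requires both before every within-cycle dose and that Section 9 drops the requirement. The text does not support that. The synopsis phrase may attach to vital signs alone, or may mean the scheduled visits, all of which carry hematology, chemistry and vital signs. It says nothing about pre-dose timing. Section 2 states that assessments are meant to be more limited than in the parent study. What remains is a request for clarification.

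**Conclusion.** The point holds as a wording inconsistency with a possible consequence for subject protection. If a partner drug is given on a day without vopratelimab, a site following the schedule would omit the test that Section 10.7 requires. This rests on two assumptions: that study drug in Section 10.7 carries the Section 6.1 meaning, and that partner-only dosing days occur, which Sections 9.2.1 and 6.1 imply but do not specify.

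The number of affected doses cannot be derived from the documents, and the minimum is zero. A reader might try to size it from the limit of 4 ipilimumab doses in Section 6.1, but that limits all ipilimumab doses, including any given with vopratelimab on Day 1. For nivolumab the documents offer no bound. Nor does counting how many statements fall on each side measure anything, since footnote 5 is one rule printed twice.

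The study is descriptive and no inference is affected. The laboratory and vital-sign question is secondary.

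**What to change.** Reword Section 5.4, and footnote 5 in both appendices, so that the test is due before each dose of any study drug, whether vopratelimab or a partner, in line with Section 10.7. The cost is a protocol wording change plus a urine or serum test on any partner-only dosing day, when the subject is already on site. If every dose falls on Day 1 with vopratelimab, there is no added burden.

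As a secondary clarification, add one sentence to Section 9.2.1 saying whether the synopsis's laboratory tests and vital signs apply on within-cycle dosing days. Either answer would do. If the answer is yes, a matching footnote in each schedule would be needed, and the cost is local laboratory work and vital signs on those days.

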9.2.2 Approximately Every 3 Months (\pm 4 Weeks)

A visit should be performed approximately every 3 months (\pm 4 weeks) to align with a scheduled study drug administration or other clinic visit. At this time, peripheral blood sampling should be performed for pharmacodynamic biomarkers. Collection of samples may be discontinued at any time per the Sponsor's discretion.

9.2.3 Every 6 Months (\pm 3 Weeks)

Disease imaging (e.g., computed tomography [CT] scan) should be performed for response assessment in accordance with institutional standard of care guidelines, but at least every 6 months (\pm 3 weeks).

9.3 End of Study

At the end of study (within 28 days \pm 7 days after last dose of study drug):

- Physical examination.
- Vital signs.
- Weight.
- Laboratory assessments including hematology and chemistry; additional laboratory measurements may be performed in accordance with institutional guidelines
- Peripheral blood sampling for pharmacodynamic biomarkers; Collection of samples may be discontinued at any time prior to end of study per the Sponsor's discretion.
- In the case of progressive disease, disease imaging (e.g., CT scan) for response assessment in accordance with institutional standard of care guidelines, but at least every 6 months (\pm 3 weeks).
- Concomitant medication review.
- AE assessment.

10 DESCRIPTION OF STUDY ASSESSMENTS

Demographic and medical history information for individual subjects will be transferred from the parent study.

10.1 Physical Examination

At all visits, a targeted physical examination will be performed per institutional guidelines. Clinically significant physical examination data will be recorded on the eCRF as AEs, as appropriate.

10.2 Vital Signs

Measurements of vital signs include blood pressure, temperature, heart rate, respiratory rate, and oxygen saturation. Vital signs should be taken prior to and at the end of each vopratelimab infusion. Clinically significant vital sign data will be recorded on the eCRF as AEs, as appropriate.

10.3 Weight

The determination of vopratelimab dose will be based on the subject's weight. Weight will be recorded on the eCRF at each visit.

10.4 Response Assessment

The anti-tumor activity of study treatment will be assessed using Response Evaluation Criteria in Solid Tumors (RECIST) version 1.1 as assessed by study investigators. Imaging for efficacy assessments will be performed in accordance with institutional standard of care guidelines, but at least every 6 months (\pm 3 weeks) and will be recorded on the eCRF.

10.5 Clinical Laboratory Evaluations

Clinical laboratory assays will include chemistry and hematology, as well as any other measurements according to institutional standard of care guidelines, performed at local laboratories according to the laboratory's normal procedures. Abnormal laboratory values that are unexpected and not explained by the subject's clinical condition should be repeated until confirmed, explained, or resolved. In the judgment of the Investigator, any clinically significant changes will be recorded on the eCRF as an AE.

10.6 Biomarkers

Pharmacodynamic biomarkers in peripheral blood, including peripheral blood mononuclear cell (PBMC)-based assays of immune cell phenotype, will be assessed approximately every 3 months (\pm 4 weeks) and at the end of treatment to determine the effect on peripheral T cells. Biomarker sampling will be recorded on the eCRF. Sample collection may be discontinued at any time per the Sponsor's discretion.

Please refer to the separate Laboratory Manual detailing the biomarker sample collection times, preparation, storage and shipping process.

10.6.1 *Retention of Samples*

If allowable by local guidelines and/or policies, all blood and PBMC samples will be retained for potential additional testing at a later date or to enable development of a companion diagnostic that would help to identify subjects most likely to benefit from vopratelimab in the future.

Samples will be retained at a secure storage facility (to be selected, qualified, and contracted by Jounce Therapeutics) in case there is need for retesting. At the end of ten (10) years after the final clinical study report is written (or some other period based on local guidelines and/or policies), or if Jounce no longer requires the samples, they will be destroyed. Analyses may be conducted by Jounce Therapeutics, Inc. or by a designated lab at their discretion.

Biospecimens will not be labeled with any personal identifiers (e.g., date of birth, initials). They will be labeled with the subject's study number to allow for future exploratory research analyses to be correlated to the study data and treatment/dose assignments.

10.7 Pregnancy Test

A serum or urine pregnancy test must be performed and reviewed on all women of childbearing potential prior to every dose of study drug. Test results will be recorded on the eCRF.

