9 OVERALL STUDY ASSESSMENTS

Duration of participation on this study will be dependent on the amount of time a subject derives clinical benefit. An End-of-study visit will be performed 28 days (\pm 7 days) after the last dose of study treatment.

9.1 Rollover Entry/Cycle 1 Day 1

Enrollment into the rollover study should occur upon exit from the parent study to avoid any interruptions in study treatment administration.

All assessments should be performed prior to vopratelimab dosing, unless otherwise noted.

- Signing of informed consent form.
- Review eligibility criteria to determine whether a subject may enter the rollover study.
- Physical examination.
- Vital signs pre-and post-infusion.
- Weight.
- Serum or urine pregnancy test for women of childbearing potential. The pregnancy test will not be required for women who are surgically sterile or who are greater than 1 year post-menopausal.
- Laboratory assessments including hematology and chemistry; additional laboratory measurements may be performed in accordance with institutional guidelines.
- Pharmacodynamic biomarkers; Collection of samples may be discontinued at any time per the Sponsor's discretion.
- Record ongoing concomitant medications and AEs.
- Study treatment (vopratelimab \pm partner drug) administration on the same dose and schedule as a subject was receiving at the time of discontinuation from the parent study. Study drug administration between the parent and rollover study should be maintained per the dose and schedule on the parent study. Any changes to the dose and schedule of vopratelimab must be in accordance with a dose and schedule previously shown to be safe and well tolerated and must be discussed with the medical monitor. Any changes to the dose and schedule of nivolumab or ipilimumab must be discussed with the medical monitor.

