Appendix 2: Schedule of Events (Every 3 Week Administration)

| Timing of Visit | Rollover Entry/ Cycle 1 Day 1 ¹ | Day 1 (\pm 3 days) of Subsequent Cycles ² | Rollover End of Study |
|---|---|---|------------------------------------|
| | | Every 3 Weeks | 28 \pm 7 days after last dose |
| Informed Consent | X | | |
| Eligibility Criteria | X | | |
| Physical Examination ³ | X | X | X |
| Weight (kg) | X | X | X |
| Vital Signs ⁴ | X | X | X |
| Pregnancy Test ⁵ | X | X | |
| Hematology | X | X | X |
| Chemistry | X | X | X |
| Other Laboratory Assessments per Standard of Care | X | X | X |
| Blood Samples for Pharmacodynamic Biomarkers | X | X ⁶ | X |
| Study Treatment Administration ⁷ | X | X | |
| Disease Imaging (e.g., CT scan) | | X ⁸ | X ⁸ |
| Concomitant Medications | X | X | X |
| Adverse Events | X | X | X |

Abbreviations: CT = computed tomography; RECIST = Response Evaluation Criteria in Solid Tumors

Footnotes:

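### Pregnancy tests stop at the last dose: none is required at the End-of-study visit, so a conception too recent to show before the final dose has no later test to find it

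*Protocol*

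**What the plan says.** Every pregnancy-test requirement in the protocol precedes a dose.

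- Section 10.7: "A serum or urine pregnancy test must be performed and reviewed on all women of childbearing potential prior to every dose of study drug".
- Section 9.2, for Day 1 of later cycles, lists "Pregnancy test for women of childbearing potential". Section 9.1 has the same item at rollover entry.
- Footnote 5 of both schedules reads "Negative serum or urine pregnancy test for women of childbearing potential prior to administration of vopratelimab on Day 1 of each treatment cycle". The pregnancy-test row is marked at entry and at later cycles, and is blank under End of Study.
- Section 5.4 also requires a negative test before each vopratelimab dose.

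The End-of-study visit is a real visit with laboratory work. Section 9 says "An End-of-study visit will be performed 28 days" after the last dose, with a 7-day margin either way. The only laboratory item in Section 9.3, apart from biomarker sampling, is "Laboratory assessments including hematology and chemistry; additional laboratory measurements may be performed in accordance with institutional guidelines". Both schedules mark a row headed "Other Laboratory Assessments per Standard of Care" at that visit, but it does not name a pregnancy test.

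On fetal risk, Section 5.4 says "There are no data regarding the effect of vopratelimab on the unborn fetus" and notes that both partner drugs carry a labeled embryo-fetal toxicity warning. Women of childbearing potential, and men whose partners could conceive, "must agree to use adequate birth control throughout their participation and for 5 months following the last study treatment". Section 10.8.7 requires a reported pregnancy to be followed to 8 weeks post-partum.

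**The concern.** A pregnancy test cannot show a conception that is only days old, so a negative pre-dose test leaves a short blind period. Repeating the test before each dose closes that period one cycle later, for every dose except the last. A woman who conceived in the days just before her final dose can test negative, receive the drug, and leave the study with no required test that would find the pregnancy.

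What is at stake is the individual woman's knowledge of the exposure and the sponsor's pregnancy follow-up. The follow-up in Section 10.8.7 is sound, but it begins only when a pregnancy is known. With no fetal data for vopratelimab, each exposed pregnancy is worth identifying early. Pregnancy is not an endpoint and the SAP plans no pregnancy output, so no analysis is at risk.

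**Working it through.** The documents state no figure to reproduce. The check is a comparison of the relevant sections, followed by visit-timing arithmetic.

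**Where tests are required**

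| Time point | Source | Test required? |
|---|---|---|
| Rollover entry, Cycle 1 Day 1 | 9.1, Appendices 1 and 2 | Yes |
| Day 1 of later cycles | 9.2, Appendices 1 and 2, footnote 5 | Yes |
| Before every dose | 5.4, 10.7 | Yes |
| End of study | 9.3, Appendices 1 and 2 | No |
| Rest of the contraception period | none | No |

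The number of required tests after the last dose is therefore 0.

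**Inputs**

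- Dosing interval: 3 × 7 = 21 days or 6 × 7 = 42 days (Appendices 2 and 1).
- End-of-study visit day, V, counted from the last dose: 28 − 7 = 21 to 28 + 7 = 35 (Section 9).
- Contraception after the last dose: 5 months, 5 × 30.44 = 152.2 days (Section 5.4).
- Detection lag, L, from conception to a positive test: 10 to 14 days. This is an assumption; the documents give none.

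**Conceptions missed at the last dose**

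Take the last dose as day 0. Its pre-dose test misses conceptions from day −L to day 0, that is, the preceding 10 to 14 days.

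Age at an End-of-study test = V − day of conception.

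- Youngest: 21 − 0 = 21 days.
- Oldest: 35 − (−14) = 49 days.

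Both exceed 14 days, so every missed conception would be detectable anywhere in the visit window. Because the youngest is 21 days old, this holds for any lag up to 21 days and does not depend on the exact value assumed.

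**What the same test would and would not reach after the last dose**

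Latest detectable conception = V − L.

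| Visit day | L = 14 | L = 10 |
|---|---|---|
| 21 | day 7 | day 11 |
| 28 | day 14 | day 18 |
| 35 | day 21 | day 25 |

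- Share of a 21-day interval covered at day 28: 14/21 = 66.7% to 18/21 = 85.7%. Over the whole visit window it runs from 7/21 = 33.3% to full coverage. Full coverage needs V of at least 21 + 10 = 31 to 21 + 14 = 35.
- Share of a 42-day interval covered at day 28: 14/42 = 33.3% to 18/42 = 42.9%. Over the whole window it is 7/42 = 16.7% to 25/42 = 59.5%. Full coverage would need V of 52 to 56, outside the window.
- Contraception days left untested: 152.2 − 25 = 127.2 to 152.2 − 7 = 145.2.

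The test would therefore close the gap before the last dose completely. It would cover the period after that dose only in part.

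**The case against.** The strongest reply is that the design is consistent. Every section ties the test to dosing because its purpose is to keep the drug from pregnant women. A test at End of Study governs no dose and cannot undo an exposure. Section 2 says assessments are deliberately lighter than in the parent study. Contraception is required throughout and for 5 months afterwards. Section 10.8.7 puts no end date on reporting a pregnancy, it makes miscarriage or congenital anomaly an SAE, and the SAE rules in Section 10.9.5 take possibly related events at any time after treatment. A pregnancy recognised later can still be followed. Finally, the change needs an amendment, and the yield may be nil.

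Much of this is accurate. The benefit is earlier knowledge, not prevented exposure, and the yield is unknown. But none of these provisions is a required test after the last dose. Contraception is also required during treatment, and the protocol still tests before every dose, so it does not treat contraception alone as enough. The reporting rules act only once someone knows of the pregnancy or of a serious outcome. Standard-of-care laboratory work, physical examination, AE review, or a Day 1 test followed by no dose may find it, but only incidentally. A lighter schedule is a fair reason not to add visits, but this visit already exists and this test is already in the protocol.

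**Conclusion.** The concern holds, as a minor point. The last dose is the only one without a later required test, and the omission is the same in Section 9.3 and both schedules. Conceptions in roughly the 10 to 14 days before that dose would be missed, and all would be detectable at the existing visit on day 21 to 35.

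The 10-to-14-day lag is assumed, but the conclusion stands for any lag up to 21 days. The number of women of childbearing potential is not stated, so the expected number of pregnancies found cannot be estimated and could be zero. Confidence is high on the omission and on the timing; it does not extend to the yield.

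**What to change.** Add a serum or urine pregnancy test for women of childbearing potential to the Section 9.3 list and to the End-of-study column of Appendices 1 and 2. Extend Section 10.7 so that the test applies at the End-of-study visit as well as before each dose. Where the End-of-study contact is by telephone, as Section 10.8.2 allows for AE collection, obtain a local or home test and record the result. Section 10.8.7 needs no change.

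The cost is one inexpensive test per woman of childbearing potential, one eCRF result field, and an amendment with IRB/EC approval under Section 13.5, plus approval of any revised consent form under Section 13.1. No visit is added and close-out is not delayed, though a woman followed up by telephone would need to arrange the test.

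The change does not cover the whole 6-week interval or the rest of the 5-month contraception period. A call at month 5 would reach further, but it would delay close-out by about 4 months (152.2 − 28 = 124.2 days) for an unknown yield. It is optional and not requested here.
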